## 7. **Research Design and Methods**

A member of the study staff familiar with the subject population will evaluate eligibility based on the approved inclusion/exclusion criteria, using patient charts. If a subject is eligible a physician on the study staff will approach the subject and/or surrogate for informed consent (please see consent procedures for more details). Demographic and clinical data will be collected during the acute hospitalization in accordance with the common data elements proposed by the TBI Common Data Element Project [29]. A drop point for deterioration for

withdrawing a subject will be a change in the GCS of greater than 2 from the previous exam.

After informed consent has been obtained, the subject will be randomized. All subjects will undergo either treatment or sham (placebo) procedures. In the sham procedure, the helmet will be placed on the patient but the LEDs will not be activated. The randomization will be set up so subjects are assigned sequentially into one of 9 groups with 10 subjects in each group. Within each group, the subject will be assigned randomly to either treatment or sham with an allocation ratio of 1:1. Once the first 10 subjects have been enrolled and have finished treatment (or sham) a DSMB (see detailed description under data safety and monitoring) will go over all of the safety data presented and make a recommendation on the continuation of the study. Subsequent DSMB meetings will take place once per year

If the subject is admitted to the ICU, he/she, will be treated according to the ICU standard of care procedures.

- Standard of care procedures include:
- Monitoring of O2/CO2 levels;
  - Avoiding hypotension;
  - Maintaining temperature within normative range;
  - Adjusting cervical collar placement if necessary;
  - Repeat CT scan if necessary;
  - Bed placement at > 30 degrees while in the ICU
  - Sedation and analgesia using recommended agents

If the subject is admitted to the ED Observation Unit, he/she will be treated according to the ED standard of care procedures.

The application of the Photomedex helmet will be in addition to but will not change the standard of care.

The following table summarizes the timing and specific assessments to be conducted in this study:

ASSESSMENTS	PRE-PROCEDURE	PROCEDURE	FOLLOW UP
Eligibility Assessment	X		
Informed Consent Form a	X		
Demographics, including date of birth, gender, and race and ethnicity	X		
Medical History	X		

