Pregnancy Test b	X		X
Investigational LLLT using the Photomedex		X	

Helmet			
Neuroimaging using Magnetic Resonance		X	X
Clinical Outcomes Assessment		X	X
AE, SAE, UADE Assessment		X	X

a If the subject regains capacity they will be re-consented at the time of follow up.

b Exclusion criteria (E4.) specific for female subjects of childbearing age.

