### 7.1. *LLLT Photomedex Helmet Device Application*

In order to maintain blinding, a study staff member not associated with analysis of the study will create a randomization code and assign treatment via an envelopment randomization system. The study staff member in charge of applying the Photomedex helmet will open each randomization envelop and once the clinician deems it is acceptable, subjects will undergo approximately 20 minutes of exposure to the Photomedex helmet within 72 hours after injury. If the subject is assigned to the sham group the LEDs will not be activated. Because the helmet uses NIR light that is invisible to the human eye, clinical staff within the room will not be able to detect whether the LEDs are activated.

The Photomedex helmet will be used up to 3 times for each subject. The first application will be as soon as possible after injury, within 72 hours. Follow up applications of the Photomedex helmet will be applied for up to 2 additional time points no sooner than 12 hours after the previous helmet application. If the subject is discharged from the hospital prior to the second helmet application, a follow up helmet application will be scheduled. If the subject wishes to have the option to complete in-person visits at his/her place of residence or another location, they will indicate this by signing the LLLT Out of Hospital Follow Up Consent Form at the time they enroll in the study.

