### 7.2. *Magnetic Resonance Imaging*

Following the 1st Photomedex helmet application, a baseline MRI will be performed, at the earliest opportunity, as soon as the subject is able to lay flat for 1 hour and the scanner is available for use. If the subject is admitted as an inpatient the scan will take place at Lunder 6 on the MGH Main Campus. If the subject is discharged from ED Observation prior to the first MRI, then the baseline MRI will take place at the Martinos Center at the Charlestown Campus. It is anticipated that the MRI will take place within 24-48h hours after enrollment and the scanning protocols themselves will take approximately 60 minutes to perform. Taking into account any necessary set up time before, during and after scanning the total time for the MRI will be approximately 60-90 minutes. If the subject is unable to undergo research-related imaging, this will be deferred until it is safe and feasible. This baseline MRI is performed

following the first application of light therapy because of the need to deliver light therapy as soon as possible after injury, and the clinical challenges of performing MRI within the first 12 hours. A designated study staff member will be responsible for gathering post-procedure follow-up data on the subject. The subjects will be followed until discharge.

Imaging protocol (for baseline and post-treatment imaging):

Subjects will be asked to lie still in a supine position for the duration of the imaging session. Head motion will be minimized during image acquisition by the use of a dedicated head coil with holder.

The MRI protocol may include the following sequences:

- 1) Localizer/Auto-aligned scout
- 2) High resolution T2 weighted imaging
- 3) FLAIR (Fluid attenuated inversion recovery) imaging
- 4) High resolution 3D T1 weighted isotropic imaging
- 5) Susceptibility-weighted imaging (SWI)
- 6) Diffusion tensor imaging (60 encoding directions)
- 7) BOLD EPI functional MRI for the evaluation of resting state functional connectivity (FC) within and between motor, visual, auditory, dorsal attention, executive control, salience and default mode networks.
- 8) Arterial Spin Labeling (ASL) brain perfusion imaging.

No contrast agent or other pharmacological substance other than ones clinically required for the subject will be given.

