Light Therapy for Moderate Traumatic Brain Injury

NCT02233413

Statistical Analysis

6.26.20

Statistical Analysis

All statistical analyses were performed using R Language for Statistical Computing (version 3.6.0). Differences and relations were considered statistically significant at $p < 0.05$. All results are presented as mean + standard deviation (S.D.) unless noted otherwise. Baseline differences across groups were compared via using one-way ANOVA for continuous variables (e.g., Age, RPQ scores) and via Chi-Square test for categorical variables. To test neuroreactivity of LLLT via its effect on the diffusion tensor parameters, we used a linear mixed effect (LME) model with treatment (light therapy vs. sham) and time point (acute, early sub-acute, late sub-acute) as fixed effects, and tract and time point nested within each patient as random effects. All patients with at least one MRI were included in this analysis. Conformity of the data to statistical assumptions were checked by investigating QQ plots of the data. LME models, which are akin to multiple regression models that can account for correlations due to repeated measures, have several advantages in this context. LME modeling allowed us to pool all our data --- i.e., across treatment groups and three time points, as well as across all 18 tracts --- to examine relationships robustly. Moreover, because the LME model allows partially repeated measures, it can accommodate data from subjects with missing timepoints (e.g., missing MRI sequences). In addition, the LME model treats each timepoint as a separate variable. Therefore, any baseline difference in DTI parameters across the LLLT and sham groups did not confound the overall analysis enabling one to robustly identify differences in DTI parameters across the treatment groups while explicitly accounting for repeated measurements, within-tract and within-subject correlations, and missing time points.

A similar LME model (treatment group and time point as fixed effects, and patient as a random effect) was used to test for the effect of LLLT on clinical symptoms). The p values for the fixed effects in the LME model were calculated using type III analysis of variance table with Satterthwaite's degrees of freedom method.

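### The SAP compares RPQ scores at baseline, but nothing in the schedule requires an RPQ before the first helmet application

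*Protocol*

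**What the plan says.** Protocol section 7 introduces its table with the words "The following table summarizes the timing and specific assessments to be conducted in this study". The columns are pre-procedure, procedure and follow-up. Eligibility, consent, demographics, medical history and the pregnancy test are marked before the procedure. The row "Clinical Outcomes Assessment" is blank there and marked under the other two columns. The imaging row, "Neuroimaging using Magnetic Resonance", carries the same marks.

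The SAP states: "Baseline differences across groups were compared via using one-way ANOVA for continuous variables (e.g., Age, RPQ scores". It then tests the effect on clinical symptoms in a mixed model with treatment group and time point as fixed effects and patient as a random effect. The protocol never names the RPQ, and the SAP does not say when the baseline score was obtained.

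**The concern.** A baseline comparison is informative only if the variable was measured before treatment could act on it. The schedule does not require this for clinical outcomes.

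If the first RPQ follows the first exposure, a difference between arms could be chance imbalance or an early effect, and the test cannot tell them apart. The absence of a difference would not show comparability either. Change from that score would not be change from the pre-treatment state.

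The timing also affects how the symptom model reads. If the score enters as a time point, it is an outcome when taken after exposure and a pre-treatment value when taken before. The documents do not let a reader tell which.

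Clinical outcome measures are part of the secondary endpoint in the Protocol Synopsis. Section 7.2 gives reasons for placing the baseline MRI after treatment (urgency, and the difficulty of early scanning). No such reason is given for symptoms, and a questionnaire needs neither a scanner nor an hour lying flat.

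**Working it through.** The plan gives no figure on this point. The check is mainly a comparison of the places where a pre-treatment score could be required.

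1. **Assessment table, Protocol section 7.** Clinical outcomes row: pre-procedure blank, procedure marked, follow-up marked. The column positions agree across rows, so this is not an artefact of the text extraction.
2. **Does a mark under procedure mean before the helmet?** Not necessarily. The imaging row has the same marks, and section 7.2 says "Following the 1st Photomedex helmet application, a baseline MRI will be performed, at the earliest opportunity". In this protocol, neither that column nor the word baseline implies pre-treatment.
3. **Acute data collection, section 7.** "Demographic and clinical data will be collected during the acute hospitalization in accordance with the common data elements" is the nearest thing to a requirement. It does not name the RPQ and sets no time relative to the helmet. Section 7.1 allows up to three applications at least 12 hours apart, so one hospital stay can include times both before and after exposure.
4. **First application, section 7.1.** "The first application will be as soon as possible after injury, within 72 hours". No symptom assessment is required first.
5. **Later contacts, section 7.3.** Day 7 call, visits at about 14-21 days, 3 months and 6 months, and a 12-month call. The first application falls within 72 hours (3 days) of injury, so all of these come after it.
6. **SAP.** RPQ is compared at baseline without a stated time. The symptom model lists no baseline RPQ covariate.

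None of these places secures a pre-treatment RPQ.

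**Size of the precision loss.** The documents give no correlation between RPQ scores over time, so r = 0.3 to 0.5 is assumed. Using a true baseline reduces the residual variance of a single follow-up score by the fraction r²:

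- r = 0.3: 0.3² = 0.09, a 9% reduction; the standard error is multiplied by √(1 − 0.09) = 0.954, about 5% smaller.
- r = 0.5: 0.5² = 0.25, a 25% reduction; the standard error is multiplied by √(1 − 0.25) = 0.866, about 13% smaller.

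**The case against.** The strongest reply is that post-treatment timing is not shown. The procedure column names a phase, and a score taken that day before the helmet goes on would fit it. The MRI is known to follow the first application only because section 7.2 says so; no text says the same for symptoms. This stands. A reader might infer that the baseline RPQ was in fact taken after treatment, so that neither outcome has a clean baseline. The documents establish that for the MRI only. For the RPQ they show only that an earlier score is not required.

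The link between the table row and the RPQ is also inferred, because the protocol does not name the instrument. The SAP, written in the past tense, implies that a score called baseline existed. That is fair, but it leaves the timing of that score unknown.

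A reader might further infer that the treatment estimate is biased, or that adjusting for a contaminated baseline removes part of the effect. The documents do not support this. Allocation is randomised 1:1, so a missing pre-treatment score does not bias the comparison between arms. The symptom model lists no baseline covariate, so nothing is adjusted away.

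Feasibility is a genuine limit. Subjects may have a GCS of 9-12, may need surrogate consent, and are to be treated quickly. Those unable to answer are likely to be the more severely injured, and a complete-case covariate would drop them. This argues for a different way of using the score. It does not argue against collecting it from subjects who can answer.

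Finally, this is a pilot whose primary endpoint is safety and feasibility. That limits the weight of the point.

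**Conclusion.** The point holds in a limited form. The SAP relies on a baseline RPQ that the protocol does not require before the first application, so the score may already reflect treatment. The randomised comparison of symptoms remains valid.

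The losses are a meaningful balance check, an interpretable change from the pre-treatment state, and precision of 9% to 25% of residual variance (about 5% to 13% of the standard error). That range depends entirely on the assumed correlation of 0.3 to 0.5, and it applies only to subjects who could answer beforehand. The verdict also assumes that the RPQ belongs to the clinical outcomes row and is the symptom measure in the SAP's second model. Both are reasonable readings, but neither is stated. The change is worth making because it is specific and inexpensive.

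**What to change.** - Name the RPQ in Protocol section 7 and mark the clinical outcomes row under the pre-procedure column as well.
- Give it after consent and before the randomisation envelope is opened, in subjects able to answer. The score, and whether it is missing, then cannot depend on allocation.
- In the SAP, enter it in the symptom mixed model as a pre-treatment time point with a common mean across arms, and let the arms differ only at later time points. Subjects without it stay in the analysis through their later scores, and the treatment effect is not averaged over a time at which none can exist.
- State in the SAP when each subject's first RPQ was taken relative to the first application. Label any score taken afterwards as post-treatment, and leave it out of the baseline comparison. For data already collected, this is the part that can still be done.

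The cost is one table mark, a short SAP paragraph and a few minutes before the first application. The downside is missing values, probably concentrated among the more severely injured. Their number should be reported by arm.

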### 7.1. *LLLT Photomedex Helmet Device Application*

In order to maintain blinding, a study staff member not associated with analysis of the study will create a randomization code and assign treatment via an envelopment randomization system. The study staff member in charge of applying the Photomedex helmet will open each randomization envelop and once the clinician deems it is acceptable, subjects will undergo approximately 20 minutes of exposure to the Photomedex helmet within 72 hours after injury. If the subject is assigned to the sham group the LEDs will not be activated. Because the helmet uses NIR light that is invisible to the human eye, clinical staff within the room will not be able to detect whether the LEDs are activated.

The Photomedex helmet will be used up to 3 times for each subject. The first application will be as soon as possible after injury, within 72 hours. Follow up applications of the Photomedex helmet will be applied for up to 2 additional time points no sooner than 12 hours after the previous helmet application. If the subject is discharged from the hospital prior to the second helmet application, a follow up helmet application will be scheduled. If the subject wishes to have the option to complete in-person visits at his/her place of residence or another location, they will indicate this by signing the LLLT Out of Hospital Follow Up Consent Form at the time they enroll in the study.

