**Table 1: Selection Criteria**

Inclusion Criteria	I1. At least 18 years old; I2. Injury within 72 hours at the time of consent; I3. Head injury requiring hospital admission;; I4. A Glasgow Coma Scale (GCS) score of 9-12 or 13-15 with abnormal imaging.
Exclusion Criteria	E1. Need for emergency neurosurgical intervention (including placement of intracranial pressure monitoring devices or drainage catheters); E2. Hemodynamic instability as determined by the clinician; E3. History of any of the following: (i) brain tumor; (ii) prior TBI occurring within the past year and requiring hospital admission; (iii) a new diagnosis within the past year of either stroke or epilepsy; (iv) an established diagnosis of any of the following neurodegenerative diseases: Alzheimer’s, Picks, Parkinson’s, Lewy body dementia, Huntington’s, amyotropic lateral sclerosis, spinocerebellar ataxia, vascular dementia, HIZ-associated dementia, dementia due to metabolic causes (Addison, Cushing, hypothyroidism, renal failure, prophyrias, Wilson, mitochondrial diseases, Wernicke-Korsakoff syndrome, and dementia of unknown etiology. E4. Pregnancy (all women of child-bearing age will need to have a negative urine pregnancy test prior to the start of the interventional portion of the study); E5. Electrical implants such as cardiac pacemakers or perfusion pumps; E6. Ferromagnetic implants such as aneurysm clips, surgical clips, prostheses, artificial hearts, valves with steel parts, metal fragments,

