In order to review the data in an unblinded fashion, we will establish a DSMB of experienced specialists from Trauma, Neurology, Radiology, Rehabilitation at MGH and Spaulding, and the Wellman Center at MGH who are not conflicted or study staff members to review the safety data. The DSMB will review the data collected after the first 10 subjects have been enrolled. The DSMB will make a recommendation as to whether or not the study should continue. If the DSMB recommends continuation of the study, subsequent DSMB review of data once per year.

Additionally, [name] MD, a neurologist at MGH and member of the DSMB will serve as an independent research monitor for the study. He will review the research protocol with the

investigators, review the monitoring plan, and review study data. If the research monitor is concerned for the safety and well-being of the subjects he/she will have the authority to stop the research protocol in progress, remove individual human subjects from a research protocol, and take whatever steps are necessary to protect the safety and well-being of human subjects until the IRB can assess the monitor's assessment. The research monitor will review all unanticipated problems involving risk to subjects or others, device-related serious adverse events and all subject deaths associated with the protocol. At a minimum, the research monitor must comment on the outcomes of the event or problem and in case of a device-related serious adverse event or death, comment on the relationship to participation in the study. The research monitor must also indicate whether he/she concurs with the details of the report provided by the principal investigator. The research monitor will provide an unbiased written report Reports for events determined by either the investigator or research monitor to be possibly or definitely related to participation and reports of events resulting in death will be promptly forwarded to the USAMRMC ORP HRPO.

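### Section 7.1 puts envelope opening before clinician clearance, so subjects may be randomised and then not treated, and the operator knows the arm before the clearance decision

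*Protocol*

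**What the plan says.** Protocol section 7 gives the sequence up to allocation. A staff member "will evaluate eligibility based on the approved inclusion/exclusion criteria, using patient charts", a physician seeks consent, and then: "After informed consent has been obtained, the subject will be randomized". No clinical clearance is named between consent and randomisation. The same section says that everyone will receive either active or sham treatment. It also sets a withdrawal point based on a change in GCS.

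Section 7.1 describes the allocation step. The code is prepared in advance: "a study staff member not associated with analysis of the study will create a randomization code and assign treatment". The person who applies the helmet then "will open each randomization envelop and once the clinician deems it is acceptable, subjects will undergo approximately 20 minutes of exposure". The order on the page is opening, clearance, exposure. Blinding of others in the room rests on the light being invisible: "clinical staff within the room will not be able to detect whether the LEDs are activated". Neither section says that the envelope stays sealed until clearance, or what happens to a subject who is randomised and then not cleared.

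Section 7.2 places the baseline MRI after the first helmet application. The SAP restricts the DTI model to patients with at least one MRI.

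**The concern.** Clearance that follows allocation creates two risks that the reverse order would avoid.

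The first is loss after randomisation. A clearance step has a purpose only if the answer can be no or not yet. Subjects are treated within 72 hours of a head injury, so a refusal, or reaching the GCS withdrawal point, could fall between the envelope and the helmet. Such a subject is randomised, untreated and probably unscanned, and the SAP's MRI rule would then remove that subject from the DTI comparison. The primary safety and feasibility endpoint counts subjects who complete the study, and no denominator is given that settles whether an untreated subject counts.

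The second is allocation knowledge. By the time the clinician decides, the operator has seen the assignment. The invisible light protects blinding during exposure but not during the decision that comes before it. Nothing keeps the operator's knowledge away from the clinician, so the decision to go ahead could come to depend on the arm. If it did, the two groups would no longer be comparable, which a power calculation cannot express.

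**Working it through.** **Order of steps, side by side**

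| Step | Section 7 | Section 7.1 |
|---|---|---|
| Eligibility | Chart review, before consent | not mentioned |
| Randomisation | After consent | Envelope opened by the operator |
| Clinician clearance | not mentioned | Written after envelope opening |
| First exposure | Follows randomisation | Follows clearance |
| First MRI | (section 7.2: after first exposure) | |
| DTI analysis set | (SAP: at least one MRI) | |

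No entry places clearance before allocation. A subject stopped between the second and fourth rows is randomised, untreated and has no scheduled route to an MRI.

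**Scale of the loss**

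Inputs from Protocol section 9: effect 25%, CV of FA 40%, required sample 82 (41 per group). From the synopsis and section 3: up to 90 subjects, which section 7 allocates 1:1, so 45 per arm. From the SAP: significance at p < 0.05. Assumptions, because the sample-size text states none of them: a two-sided test and 80% power. The share left untreated is also assumed, at 5% and 10%, equal in both arms.

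1. Standardised effect: d = 0.25 / 0.40 = 0.625.
2. The plan's own figure: n per arm = 2 × (1.960 + 0.842)² / 0.625² = 40.2, rounded up to 41. The rule of thumb 16 / d² = 16 / 0.390625 = 40.96 also gives 41. Both give 82 in total, so the stated figure reproduces.
3. Margin: 90 − 82 = 8 subjects, and 8 / 90 = 8.9%.
4. Power is from the noncentral t distribution with 2n − 2 degrees of freedom and noncentrality d × √(n / 2). At n = 45, noncentrality is 0.625 × √22.5 = 2.965 and power is 83.5%.
5. If untreated subjects **leave the analysis**, d stays at 0.625 and n becomes 45 × (1 − k).
6. If untreated subjects are **kept as randomised**, n stays at 45 and d becomes 0.625 × (1 − k).

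| Untreated share k (assumed) | Excluded: n per arm | Excluded: power | Kept: d | Kept: power |
|---|---|---|---|---|
| 0% | 45 | 83.5% | 0.625 | 83.5% |
| 5% | 42.75 | 81.5% | 0.594 | 79.5% |
| 10% | 40.5 | 79.3% | 0.563 | 75.1% |

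The two treatments of these subjects are alternatives, and their losses must not be added. The excluded column matches the SAP's MRI rule more closely. These are two-group calculations on the plan's sample-size basis, not simulations of the SAP's mixed model, so they show scale only.

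**The case against.** The strongest reply is that the sentence in section 7.1 may not be meant as a sequence. The clearance clause governs when exposure starts and could mean only that treatment waits for a suitable moment within the 72 hours. Section 7 says merely that randomisation follows consent, which fits either order, and it states the intention that all subjects undergo a procedure. This has force: the text does not expressly fix the order. But no section puts clearance first or keeps the envelope sealed until then. If the wording is only loose, the moment of allocation is undefined and the same sentence is needed.

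The pregnancy test is a weak additional route. Table 1 requires a "negative urine pregnancy test prior to the start of the interventional portion of the study", which does not say before randomisation. However, the assessment table in section 7 lists the test as pre-procedure alongside eligibility and consent, and pregnancy is an exclusion criterion. The documents do not place the test after randomisation.

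Several stronger readings are tempting and are not supported:

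- A reader might infer that some subjects were in fact randomised and left untreated. No document reports this or gives a rate.
- A reader might take the operator to be the only unblinded person. The creator of the code also knows the allocation, and section 12.1 says: "In order to review the data in an unblinded fashion, we will establish a DSMB".
- A reader might place the operator at the clinician's decision. Section 7.1 says only that "The study staff member in charge of applying the Photomedex helmet will open each randomization envelop". It does not say where or with whom the clinician decides.
- A reader might start from 41 per arm, dilute the effect, and quote power of 75.7% or 71.1%. That ignores the planned 90, and it keeps in the analysis subjects whom the MRI rule would probably remove.

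**Conclusion.** The point stands as a weakness in the written sequence. Envelope opening is placed before clearance, nothing requires clearance before randomisation, and nothing shields the decision from the operator's knowledge of the arm. Subjects may therefore be lost after randomisation, and arm-dependent cancellation of the first application is possible. The documents do not show that either occurred.

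The cost in power is modest. At an assumed 5% or 10% untreated it is about 2 or 4 percentage points if those subjects drop out (83.5 − 81.5 = 2.0; 83.5 − 79.3 = 4.2). It is about 4 or 8 points if they are kept with a diluted effect (83.5 − 79.5 = 4.0; 83.5 − 75.1 = 8.4). The 8-subject margin absorbs most of the first loss. These figures rest on the plan's 25% effect and 40% CV, a two-sided 5% test, and equal loss in both arms. Loss from the DTI analysis is probable rather than certain, since no section forbids scanning an untreated subject. The better reason to change the text is that the allocation step is left unprotected.

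**What to change.** State in Protocol sections 7 and 7.1 that the sealed envelope is opened only after (a) documented clearance by a clinician blinded to allocation and (b) completion of all eligibility checks, including any required pregnancy test. State also that it is opened immediately before the first application and out of sight of clinical staff, and that this opening is the moment of randomisation. Refusals at the clearance step then occur before randomisation and remove no randomised subject.

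A few subjects may still be randomised and not treated, so the SAP should add one line on how they are counted and analysed.

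The cost is a sentence or so in each section. The change needs no extra visit or staff and alters no treatment rule, so it is a free improvement. Its limit should be acknowledged: the helmet may be applied up to three times, and the operator already knows the arm before the second and third applications, so decisions about those are not protected.
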